4.2. Exclusion Criteria

To be enrolled in the study, potential subjects must not have any of the following exclusion criteria:

Disease-Related

1. Primary refractory disease defined as nonresponsive in patients who have never achieved a minimal response or better with any therapy.
2. History of plasma cell leukemia, primary amyloidosis, POEMS syndrome within 12 months prior to first administration of study treatment.

Concurrent Conditions

3. Recent prior chemotherapy:
 - a. Alkylators (eg, melphalan, cyclophosphamide) and/or anthracyclines <21 days prior to first administration of study treatment.
 - b. High dose corticosteroids, IMiDs or proteasome inhibitors <14 days prior to first administration of study treatment.
 - c. Monoclonal antibody <14 days prior to first administration of study treatment.
4. Prior exposure to BTK inhibitors.
5. Prior exposure to pomalidomide (except Treatment Arm C).
6. History of serious hypersensitivity reactions to prior thalidomide, lenalidomide or pomalidomide.
7. History of other malignancies, except:
 - a. Malignancy treated with curative intent and with no known active disease present for ≥ 3 years before the first dose of study drug and felt to be at low risk for recurrence by treating physician.

- b. Adequately treated non-melanoma skin cancer or lentigo maligna without evidence of disease.
- c. Adequately treated carcinoma in situ without evidence of disease.
8. Peripheral neuropathy Grade ≥ 2 with pain at Screening.
9. Concurrent systemic immunosuppressant therapy (eg, cyclosporine A, tacrolimus, etc., or chronic administration of >20 mg/day of prednisone or equivalent) within 28 days of the first dose of study treatment.
10. Recent infection requiring systemic treatment that was completed <7 days before the first dose of study treatment and/or uncontrolled active systemic infection.
11. Unresolved toxicities from prior anti-cancer therapy, defined as having not resolved to [CTCAE \(version 4.03\)](#), Grade ≤ 1 or to the levels dictated in the inclusion/exclusion criteria with the exception of alopecia.
12. Known bleeding disorders (eg, von Willebrand's disease or hemophilia).
13. History of stroke or intracranial hemorrhage within 6 months prior to enrollment/randomization.
14. Known history of human immunodeficiency virus (HIV) or active with hepatitis C virus (HCV) or hepatitis B virus (HBV). Subjects who are positive for hepatitis B core antibody, hepatitis B surface antigen, or hepatitis C antibody must have a negative polymerase chain reaction (PCR) result before enrollment/randomization. Those who are PCR positive will be excluded.
15. Major surgery within 4 weeks of first dose of study treatment.
16. Any life-threatening illness, medical condition including uncontrolled Diabetes Mellitus, or organ system dysfunction that, in the opinion of the investigator, could compromise the subject's safety or put the study outcomes at undue risk.
17. Currently active, clinically significant hepatic impairment (\geq mild hepatic impairment according to the Child Pugh classification [[Appendix 10](#)])
18. Currently active, clinically significant cardiovascular disease, such as uncontrolled arrhythmia or class 3 or 4 congestive heart failure as defined by the New York Heart Association Functional Classification; or a history of myocardial infarction, unstable angina, or acute coronary syndrome within 6 months prior to enrollment/randomization.
 - QTc ≥ 470 msec calculated using Fridericia formula (QTcF) at Screening.
19. Unable to swallow capsules, malabsorption syndrome, disease significantly affecting gastrointestinal function, resection of the stomach or small bowel, symptomatic inflammatory bowel disease or ulcerative colitis, or partial or complete bowel obstruction.
20. Requires treatment with a strong cytochrome P450 (CYP) 3A4 inhibitor (see [Appendix 5](#)).
21. Women who are pregnant or breast-feeding.
22. Unwilling or unable to participate in all required study evaluations and procedures.

23. Unable to understand the purpose and risks of the study and to provide a signed and dated informed consent form (ICF) and authorization to use protected health information (in accordance with national and local subject privacy regulations).

4.2.1. Exclusion Criteria for Open-Label Sub-Study Arm C (Phase 2b)

To be enrolled in the sub-study, each potential subject must not meet any exclusion criteria defined in [Section 4.2](#) EXCEPT for exclusion criteria 5 which is related to prior pomalidomide and does not apply for the sub-study Arm C.

5. TREATMENT OF SUBJECTS

5.1. Phase 1 Dose Escalation and Stopping Rules

Phase 1 will follow a 3+3+3 dose escalation design with 3-9 subjects treated at each dose level. Before determining the Phase 2b dose, at least 6 subjects will be treated at the MTD or highest dose level tested. The DLT observation period includes Cycle 1 and all pre-dose assessments per protocol on Day 1 of Cycle 2. The dose will be selected as the Phase 2b dose if the subject incidence of DLTs during the DLT observation of study treatment is <33% (ie, $\leq 1/6$ or $\leq 2/9$ subjects with a DLT). If there are ≥ 3 subjects with a DLT in Cohort 1, then the next lower dose level (Cohort -1) will be enrolled. In the event that Cohort -1 will be considered the Phase 2b dose, the Sponsor may choose not to continue with Phase 2b enrollment as outlined in the protocol (for dose levels, see [Table 1](#)).

Dose Escalation: A minimum of three subjects will be enrolled within each cohort. The DMC will evaluate each individual cohort prior to any dose escalation or de-escalation ([Table 1](#)). Before applying the dose escalation rules, 3 subjects must have completed the first cycle of therapy and have been evaluated for toxicity as defined by the DLT observation period. If no DLT is observed in the first three subjects, then dose escalation will take place. If one of three subjects experience a study treatment-related DLT during the first treatment cycle, the same cohort will be expanded to six subjects, and if two of the six experience a DLT it will be expanded to 9 subjects. If 1/6 or 2/9 subjects experiences a study treatment related DLT during the first treatment cycle, dose escalation will occur and the next cohort may be enrolled. If at any time during a cohort, ≥ 3 subjects experience a study treatment related DLT, the MTD will have been exceeded, and additional enrollment within the cohort will cease. If there are 3 DLTs in Cohort 1, Cohort -1 will be enrolled. The MTD will be defined as the highest dose cohort at which <33% of subjects in a cohort experience a study treatment related DLT. If the MTD is not reached, the maximum administered dose (MAD) will be established as the highest dose level tested per protocol.

Table 1: Dosing Levels and Cohorts

Dose Level	Cohort	Ibrutinib ^a	Pomalidomide ^b	Dexamethasone ^c
-1	-1	420 mg once daily	4 mg	40 mg
1 (Starting Dose)	1	560 mg once daily	4 mg	40 mg
2	2	840 mg once daily	4 mg	40 mg

a. Ibrutinib will be administered PO starting on Day 1 of Cycle 1, dosing is continuous thereafter (without interruption).

b. Pomalidomide will be administered PO on Days 1 – 21 of a 28-day cycle.

c. Dexamethasone will be administered PO once weekly. Dose will be 20 mg weekly in those >75 years of age

Missed doses of ibrutinib, pomalidomide and dexamethasone will not be made up.

Note: In the dose finding portion, if a subject is non-compliant with the prescribed therapy or ends treatment within the first cycle for reasons other than study drug(s) related toxicity, ie, withdraws consent, they will be replaced. Any subject that misses >5 doses of ibrutinib or >3 doses of pomalidomide for reasons other than toxicity during the first cycle will be replaced. The review and confirmation of DLTs will be performed by the independent DMC and the decision to proceed with either Phase 2 initiation or dose escalation/de-escalation will be made in collaboration with the Sponsor.

5.1.1. Definition of Dose Limiting Toxicity (DLT)

The assessment of DLT will follow the guidelines provided in the [CTCAE \(version 4.03\)](#).

A DLT is defined as:

Hematologic:

- Grade 4 neutropenia (ANC <500/mm³) lasting for >7 days
- Febrile neutropenia (ANC <1,000/mm³ with a fever ≥38.3°C)
- Grade 4 thrombocytopenia (<25,000/ mm³) that persists for >7 days, despite holding treatment
- Grade 3 thrombocytopenia associated with Grade ≥2 bleeding or requiring RBC or >1 platelet transfusion

Non-Hematologic:

- Any Grade 3 or higher non-hematologic AE where relationship to study drug(s) cannot be ruled out
- Grade ≥3 nausea, vomiting, or diarrhea uncontrolled by maximal supportive care and persisting >7 days
- Grade ≥3 rash if symptomatic and requiring systemic intervention other than drug hold; unless hold is for >7 days
- Any Grade 4 or desquamating rash

- Treatment delay of any drug > 7 days for toxicity; unless toxicity can be solely attributed to pomalidomide

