6. CONCOMITANT MEDICATIONS/PROCEDURES

6.1. Concomitant Medications

6.1.1. Permitted Concomitant Medications

Supportive medications in accordance with standard practice (such as for emesis, diarrhea, etc.) are permitted.

Usage of antimicrobial prophylaxis in accordance with standard practice (eg, ASCO guidelines [[Flowers 2013](#)]) is permitted and should be considered in subjects who are at increased risk for opportunistic infections.

Erythropoietic growth factors (eg, erythropoietin) and hematopoietic growth factors are allowed per institutional policy and in accordance with the ASCO guidelines ([Smith 2006](#)).

Transfusional support (packed red blood cells and platelets) may be given in accordance with institutional policy. The use of myeloid growth factors is encouraged when ANC is less than 800/ μ L at the discretion of the treating physician. Primary prophylaxis for the prevention of neutropenia is highly recommended in subjects who are at high risk based on age, medical history and disease characteristics. **In Phase 1:** Erythropoietic and hematopoietic growth factors as well as transfusional support (platelets) should not be given during the DLT assessment window, but is permitted at the Investigator's discretion if a subject experiences a hematologic DLT as per the criteria outlined.

After consultation with the Medical Monitor the following may be considered; localized hormonal or bone sparing treatment for non-B-cell malignancies, and localized radiotherapy for medical conditions other than the underlying B-cell malignancies.

Short courses (≤ 14 days) of steroid treatment for non-cancer-related medical reasons (eg, joint inflammation, asthma exacerbation, rash, antiemetic use and infusion reactions) at doses that are

clinically indicated are permitted in addition to those administered as study treatment per protocol.

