11.2.6.1. Major Hemorrhage

Major hemorrhage is defined as any of the following:

- Any treatment-emergent hemorrhagic AEs of Grade 3 or higher*
- Any treatment-emergent serious adverse event of bleeding of any grade.
- Any treatment-emergent central nervous system hemorrhage/hematoma of any grade.

*All hemorrhagic events requiring transfusion of red blood cells should be reported as Grade 3 or higher AE per CTCAE (version 4.03).

Events meeting the definition of major hemorrhage will be captured as an event of special interest according to Section 11.2.6 above.

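### The two platelet rows of the DLT definition are not monotone: a short Grade 4 episode can go uncounted where Grade 3 with the same complication counts, and one transfusion trigger sits awkwardly with Section 6.1.1

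*Protocol*

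**What the plan says.** Protocol Section 5.1.1 has two thrombocytopenia rows.

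- Grade 4, given there as a count below 25,000, is a DLT if it is one "that persists for >7 days, despite holding treatment". The row has no bleeding or transfusion branch.
- The other row opens "Grade 3 thrombocytopenia associated with Grade" 2 or higher bleeding and continues "or requiring RBC or >1 platelet transfusion". It has no duration condition.

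The same list contains a general row: "Any Grade 3 or higher non-hematologic AE where relationship to study drug(s) cannot be ruled out". It also counts a delay of any drug beyond 7 days for toxicity, unless the toxicity is attributable to pomalidomide alone.

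Section 6.1.1 adds a Phase 1 restriction: growth factors and "transfusional support (platelets) should not be given during the DLT assessment window", with use allowed at the investigator's "discretion if a subject experiences a hematologic DLT as per the criteria outlined".

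Section 5.1 accepts a dose level when DLT incidence is below 33% (at most 1/6 or 2/9) and treats three or more DLTs as exceeding the MTD. The SAP (Section 1.1) repeats the limit, keeps MTD/MAD as a primary objective, and plans a DLT listing (Section 5) without a DLT definition of its own.

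**The concern.** A toxicity rule should not score a worse course as better tolerated than a milder one. Here the complication branch names Grade 3 alone, while neighbouring rows for nausea, rash and other non-hematologic events use wording that takes in higher grades. A subject at 15,000 for 6 days with Grade 2 bleeding and two platelet transfusions meets neither platelet row. The same course at 30,000 is a DLT.

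Bleeding is a stated ibrutinib risk (Section 1.2.4.1), and cohorts are small enough for one subject to decide a classification.

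The second issue is smaller. One trigger for a hematologic DLT is a platelet-transfusion requirement, yet Section 6.1.1 reserves platelets in the window for subjects who already have such a DLT.

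**Working it through.** **1. The plan's own limit.** 1/6 = 16.7% and 2/9 = 22.2% are below 33%. 3/9 = 33.3% is not. The limit therefore agrees with the three-DLT stop in Section 5.1.

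**2. The two platelet rows side by side.**

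| Course in Cycle 1 | Grade 3 row | Grade 4 row | Caught by another row? |
|---|---|---|---|
| Grade 3, Grade 2 bleeding, any duration | DLT | n/a | not needed |
| Grade 4, more than 7 days despite hold | n/a | DLT | not needed |
| Grade 4, 7 days or less, Grade 3 or higher bleeding | no | no | yes, general non-hematologic row, if relationship cannot be ruled out |
| Grade 4, 7 days or less, bleeding that needs red cells | no | no | yes, on the same condition: Section 11.2.6.1 says "All hemorrhagic events requiring transfusion of red blood cells should be reported as Grade 3 or higher AE" |
| Grade 4, 7 days or less, Grade 2 bleeding without red cells | no | no | only by the delay row |
| Grade 4, 7 days or less, more than one platelet transfusion | no | no | only by the delay row |
| Grade 4, 7 days or less, red cells without bleeding | no | no | only by the delay row |

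The last three lines are the residual gap.

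**3. What the delay row can catch.** It covers any drug.

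- *Pomalidomide.* Table 4 interrupts it for the rest of the cycle at Grade 4. A hold from Day 8 loses the doses of Days 8 to 21, which is 14. A hold from Day 15 loses 7 doses, with 14 calendar days to the next cycle. Section 5.1.1 does not say whether such an interruption is a delay, and toxicity due to pomalidomide alone is exempt.
- *Ibrutinib.* Table 2 holds it until platelets exceed 25,000 with no Grade 2 or higher bleeding. Continued bleeding lengthens the hold, but it can still end within 7 days.

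**4. Documenting the duration.** Cycle 1 hematology is scheduled on Days 1, 8, 15 and 22 (Section 8.3, Appendix 1). Two consecutive scheduled counts span 7 days, which is not more than 7. Showing a longer episode takes a third visit or an unscheduled count.

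**5. Effect of one uncounted subject (Section 5.1 rules).**

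- 1/3 (expand to six) becomes 0/3 (escalate).
- 2/6 = 33.3% (expand to nine) becomes 1/6 = 16.7% (escalate).
- 3/9 = 33.3% (MTD exceeded) becomes 2/9 = 22.2% (accepted).

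**6. Sensitivity of the rule, for scale only.** With per-subject DLT probability p and q = 1 − p, the chance of escalating is q³ + 3pq⁵ + 9p²q⁷ if 2/3 stops the cohort, and q³ + 3pq⁵ + 12p²q⁷ if 2/3 expands it. Section 5.1 does not state which applies. A true rate of 33% and the uncounted points below are assumptions.

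| Points uncounted | 2/3 expands | 2/3 stops |
|---|---|---|
| 0 | 0.514 | 0.494 |
| 2 | 0.560 | 0.538 |
| 5 | 0.630 | 0.607 |
| 10 | 0.745 | 0.720 |

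**7. The transfusion branch against Section 6.1.1.** The Phase 1 restriction on transfusion names platelets only. The bleeding and red-cell branches of the Grade 3 row can therefore be reached without conflict. If *requiring* means clinical need, the platelet branch can be reached too. If it means receipt, a subject with no prior hematologic DLT reaches it only by departing from Section 6.1.1.

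**The case against.** The strongest reply is that the gap is small and mostly covered. Much of that stands. Serious bleeding and bleeding that needs red cells reach the general non-hematologic row. The delay row reaches some of the rest, including through an ibrutinib hold prolonged by bleeding. A subject recovering through the Grade 3 range while still bleeding may also qualify.

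A second reply is that Section 5.4.4 and Table 4 describe Grade 3 as a count below 50,000 with no lower bound, so 15,000 with bleeding would qualify. That reading is possible, but Section 5.1.1 does not state it, and both other places list Grade 4 separately. Their purpose is dose modification, so differing from them is not in itself an error. Independent confirmation of DLTs by the DMC (Section 5.1) helps, but nothing lets the DMC depart from the written criteria.

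A reader might infer that a site cannot comply with Sections 5.1.1 and 6.1.1 together. The documents do not support that. Section 5.1.1 classifies events and does not order transfusions, Section 6.1.1 says *should not*, and only one of three branches is touched.

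A reader might also take the reported thrombocytopenia rates as the size of the gap: 19–22% Grade 3/4 with pomalidomide-dexamethasone and 18% Grade 3 or higher with ibrutinib-carfilzomib. They are not. They count Grade 3 and above together in other studies, not Grade 4 of 7 days or less with one of these complications in Cycle 1.

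**Conclusion.** The point holds in a limited form. On its wording, Section 5.1.1 can score a short Grade 4 episode as no DLT when Grade 3 with the same complication is a DLT. The uncovered cases are Grade 2 bleeding, more than one platelet transfusion, or red cells without bleeding, where the delay row does not apply. The platelet-transfusion trigger is circular with Section 6.1.1 only if *requiring* means receipt.

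The documents give no frequency for the gap, and nothing in them shows that any treated subject fell into it. Its weight comes from cohort size, since one subject moves 3/9 to 2/9. The probabilities in the sensitivity table rest on assumed rates.

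A reader might go further and infer that a dose was wrongly cleared or that Phase 2b subjects were exposed. The SAP (Sections 1 and 6) rules out the second, because Phase 2 was not initiated after 11 subjects were treated in Phase 1. The first has no support in the documents. What remains exposed is the MTD/MAD conclusion and the DLT listing.

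**What to change.** 1. The sponsor should reconcile the two platelet rows of Section 5.1.1 with each other, stating how a complication named in the Grade 3 row is classified when the count is Grade 4.
2. Reconcile the platelet-transfusion branch with Section 6.1.1, including whether *requiring* means clinical need or receipt.
3. Before the MTD/MAD statement and DLT listing are final, re-read the Cycle 1 platelet, bleeding and transfusion data of the 11 treated subjects against the reconciled rows. Report any subject whose classification depends on the reading, with the literal classification beside it, so that the re-read is not a silent re-scoring.

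Which clinical rule governs is for the sponsor. The cost is a short clarification in the SAP or study report and a small re-read of collected data. The DLT count may become slightly less favourable.

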5.2. Randomization and Blinding

Subjects who satisfy all the inclusion/exclusion criteria are eligible to enter the study.

Phase 1:

Phase 1 is an open-label study; there will be no randomization or stratification of subjects.

Phase 2b:

After the subject has completed all baseline (Screening) procedures and satisfied all requirements of the inclusion/exclusion criteria, study site personnel will submit the Eligibility Worksheet (EW) to the Medical Monitor or Sponsor designee for approval. In order to begin treatment, study personnel will register the subject into the IWRS to have drug assigned to that subject. The first dose of study drug should be administered after randomization, but no more than 3 business days after the subject has been randomized by IWRS.

Approximately 195 subjects will be randomized in a 1:1 ratio to the 2 treatment arms:

- Treatment Arm A: ibrutinib in combination with pomalidomide and dexamethasone
- Treatment Arm B: placebo in combination with pomalidomide and dexamethasone

Central randomization will be implemented in this study. Randomization will be stratified using the following stratification factors and subjects will be randomized in a 1:1 ratio to receive either ibrutinib in combination with pomalidomide and dexamethasone or placebo in combination with pomalidomide and dexamethasone:

- a. Number of prior systemic treatment regimens (2-3 vs. ≥ 4)
- b. Last regimen (no IMiD/PI vs. IMiD or PI vs. IMiD and PI)
- c. Age: ≤ 75 vs. > 75 years

The IWRS will assign a unique treatment code, which will dictate the treatment assignment and matching study drug kit for the subject. The requestor must use his or her own user identification and personal identification number when contacting the IWRS, and will then give the relevant subject details to uniquely identify the subject.

Subjects eligible for open-label sub-study Arm C will be enrolled using the IWRS to obtain a unique treatment code.

Blinding

This is a double-blind study; therefore, subjects, investigators, and the Sponsor's study team members will remain blinded to study treatment assignment. The investigator will not be provided with randomization codes. The codes will be maintained within the IWRS, which has

the functionality to allow the investigator to break the blind for an individual subject. Data that may potentially unblind the treatment assignment (ie, study drug plasma concentrations) will be handled with special care to ensure that the integrity of the blind is maintained and the potential for bias is minimized. This may include making special provisions, such as segregating the data in question from view by the investigators, clinical team, or others as appropriate until the time of database lock and/or unblinding.

Under normal circumstances, the blind should not be broken. The blind should be broken only if specific emergency treatment/course of action would be dictated by knowing the treatment status of the subject. In such cases, the investigator may in an emergency determine the identity of the treatment by contacting the IWRS. It is recommended that the investigator contact the Sponsor or its designee, if possible, to discuss the particular situation before breaking the blind. Telephone contact with the Sponsor or its designee will be available 24 hours per day, 7 days per week. In the event the blind is broken, the Sponsor must be informed as soon as possible. The date, time, and reason for the unblinding must be documented by the IWRS and in the source document. The documentation received from the IWRS indicating the code break must be retained with the subject's source documents in a secure manner. A subject whose treatment assignment has been unblinded may continue the study treatment if receiving clinical benefit, and the subject should continue to return for scheduled study evaluations. The single-blind (ie, subject remains blinded to treatment assignment) should be maintained provided the subject's safety is not compromised.

At the time of the interim analysis, the randomization codes and, if required, the translation of randomization codes into treatment and control groups will be disclosed to those authorized and only for those subjects included in the interim analysis.

All subjects eligible for the sub-study Arm C will be treated in an open-label fashion.

